review the participant’s medical information and provide an influenza diagnosis based on clinical judgement. If probable influenza is diagnosed, the 98point6 provider will confirm that antiviral treatment is appropriate. If appropriate, drug eligible study participant will subsequently receive a single dose of BXM delivered to their household via rapid delivery service for therapy initiation within 48 hours of symptom onset. Concurrently, the ill individual will collect a Study Day 0 nasal swab sample that will be mailed back to the laboratory for further testing. Additional nasal swabs will be collected at Study Day 2-3 and Study Day 5-7. If influenza is not diagnosed, the ill individual will provide one self-collected or parent/permanent legal guardian-collected nasal swab specimen that will be mailed back to the laboratory for further testing, and the household will remain enrolled and all study participants in the household will continue to self-monitor for presence of symptoms. Once an eligible study participant receives BXM, no additional household members will be eligible to receive BXM; the household will be able to continue monitoring for onset of symptoms, as well as self-testing and swabbing when symptoms develops, but the household will no longer be able to receive BXM delivery.

Figure 1. Study schema

Symptom Table

Feeling Feverish	Muscle or Body Aches
Headache	Rash
Sore Throat or Itchy/Scratchy Nose	Runny/stuffy nose
Feeling More Tired Than Usual	Muscle or body aches
Nausea or Vomiting	Increased trouble with breathing
Ear Pain or Ear Discharge	Diarrhea

The study is being conducted in the Seattle, WA area over one influenza season. The goal is to have 250 households comply with full study procedures. Of these, 25% are estimated to have an individual in the household diagnosed with influenza based on estimates from previous household studies.^{23, 28-29}

A table for influenza attack rates by household size is provided below.

Household attack rate	Total households enrolled	Primary cases	Secondary cases (mean household size 5)	Secondary cases (mean household size 4)	Secondary cases (mean household size 3)
25%	250	63	45-96	34-72	23-48
20%	250	50	36-76	27-57	18-38
10%	250	25	18-38	14-29	9-19
Mean household size includes case.					
Secondary attack rate 18-38%, secondary cases presented as a range based on these high and low bounds. ³⁰⁻³²					

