The University of Washington is the sponsor of the study which is supported by an anonymous funder who does not have any ownership over the management and conduct of the study, the data, or the rights to publish.

III. Objectives

The objective of the study is to measure the proportion of individuals who are initiated on antiviral therapy within 48 hours of symptom onset using a home-based self-test, followed by a telehealth consultation to diagnose influenza and home delivery of antivirals

Primary Outcome Measures

The primary outcome measure will be the proportion of eligible individuals who initiate antiviral therapy at home within 48 hours of symptom onset utilizing a home-based test and the telehealth app for influenza diagnosis and rapid home-delivery of antivirals. It will be calculated using binomial regression with log link, where the number of drug eligible influenza-diagnosed individuals, defined as the number of individuals eligible to receive BXM with both self-test positive influenza and laboratory-confirmed influenza, reporting administration of the study drug within 48 hours of symptom onset is divided by the total number of drug eligible individuals with both self-test positive influenza and laboratory-confirmed influenza.

Secondary endpoints:

- Proportion of individuals who test positive for influenza using the home-based test within 48 hours of symptom onset
- Proportion of individuals with a positive home-based influenza self-test who have a positive test confirmed by the central laboratory
- Sensitivity and specificity of a self-test compared to a laboratory-based molecular influenza test
- Proportion of individuals who are delivered antivirals within 48 hours of symptom onset
- Proportion of individuals who self-report administration antiviral therapy within 48 hours of symptom onset
- Symptom duration and severity among drug eligible and drug ineligible influenza-positive individuals
- Proportion of families with influenza infection diagnosed within 7 days of an index case (another influenza-positive household member)
- Viral quantity and duration of viral RNA detection among drug eligible and drug ineligible influenza-positive participants
- Proportion of drug ineligible study participants seeking medical care for respiratory illness symptoms
- Proportion of individuals who choose to take a self-test among those who are eligible to take a self-test

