- Within-host variation in influenza strains between the first and the third viral swab
- Cost effectiveness, assessed using health resource utilization (visit to clinic, hospital, pharmacy, emergency department) and school and work absenteeism
- Proportion with antiviral resistance, assessed by genetic sequencing of influenza strains from the drug eligible and drug ineligible study participants

Hypothesis

Primary hypothesis:

- A home-based approach to influenza infection control will result in a large percentage of drug eligible individuals diagnosed with influenza initiating antiviral therapy within 48 hours of symptom onset.

Secondary hypotheses:

- Home-based approach to influenza infection control and rapid delivery of antiviral therapy will decrease symptom severity in the drug eligible individuals diagnosed with influenza that administer antiviral therapy within 48 hours of symptom onset compared to drug eligible, influenza-infected individuals that administer antiviral therapy greater than 48 hours after symptom onset.
- Home-based approach to influenza infection control and rapid delivery of antiviral therapy will decrease the duration of viral RNA detection in the drug eligible, influenza-infected individuals that administer antiviral therapy within 48 hours of symptom onset compared to drug eligible, influenza-infected individuals that administer antiviral therapy greater than 48 hours after symptom onset.

IV. Study Population

The study will be conducted in households with at least 3 members, where at least 2 of these members must be eligible to receive BXM, in the Seattle area. Participants aged 12 years or older, weighing at least 40 kg, will be drug eligible. Participants of any age that reside in the same household as the case at least 4 days per calendar week will be drug ineligible study participants. Drug eligible study participants will receive baloxavir intervention when appropriate,

and all drug eligible and drug ineligible participants will receive a 7-day follow-up from the study team per illness episode.

Study size

The study is being conducted in the Seattle, WA area over one influenza season. The goal is to enroll 250 households, with enrollment occurring prior to and during the annual influenza season.

Household enrollment criteria

The household must meet all the following enrollment criteria:

Household inclusion criteria

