- Group of at least 3 individuals of any ages defined as at least 3 persons residing at the same address for at least 4 days per calendar week
- Household group utilizes common household areas
- At least 2 household members meeting all individual inclusion/exclusion criteria listed below and willing to participate (e.g. at least two members of the household are 12 years of age or older)
- At least one member of the household has a smartphone

Household exclusion criteria

Within eligible households, individuals meeting any of the following criteria will be excluded:

- Previous documentation of an influenza infection prior to or during the annual influenza season in any household member prior to enrollment

Study participants

Inclusion criteria for eligible study participants include:

Inclusion criteria for drug eligible study participants:

- Resident of a household with 3 or more members (including eligible cases) for 4 or more days a calendar week
- Age 12 years or older weighing at least 40 kg (greater than 88 pounds)
- Willing and able to take study medication
- Willing to comply with all study procedures
- English-speaking
- Able to provide written, informed consent and/or assent (if applicable)
- Permanent mailing address that is available for study staff to mail necessary materials

Inclusion criteria for drug ineligible study participants:

- Resident of a household with 3 or more members (including eligible cases) for 4 or more days a calendar week
- Willing to comply with all study procedures
- English-speaking
- Able to provide written, informed consent and/or assent (if applicable)

Exclusion criteria

Individuals meeting any of the following criteria will be excluded from being drug-eligible, but may still participate in the study by submitting swabs:

- Any serious or uncontrolled medical disorder or active infection that, in the opinion of the investigator, may increase the risk associated with study participation or study drug administration
- Individuals with hypersensitivity to baloxavir
- Any individual that has one or more of the following conditions:
 - Pregnant
 - Currently lactating
 - Immunosuppressed or immunocompromised (by disease or medication)
 - Cancer
 - Liver disease
 - Kidney disease

Individuals meeting the following criteria will be excluded from being drug-eligible, and will not participate in submitting swabs:

- Age younger than 3 months

Withdrawal criteria

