Person-to-person transmission: We will use the CDC definition for influenza transmission that refers to the ability of an influenza virus to spread from one person to another, most commonly through large or small droplets containing influenza virus that are expelled when a sick person is coughing or sneezing.

XI. Statistical Analyses

The primary objective is to precisely estimate the proportion of drug eligible individuals with an influenza diagnosis who initiate treatment within 48 hours. We define precision in terms of the width of a 95% confidence interval. The width of a 95% CI will be less than or equal to $\pm 1.96 \cdot 0.5/\sqrt{n}$ where n is the number of individuals who test positive for flu. With 250 households participating and an attack rate of 25% we expect 63 individuals with confirmed influenza infection. This will give a 95% CI for the proportion initiating treatment of ± 0.12 or less.

The proportion of drug eligible individuals receiving the drug and initiating treatment within 48 hours of symptom onset using home-based self-test and delivery methods will be estimated. Binomial regression with log link will be used to calculate the relative risk of receiving and initiating treatment within 48 hours by demographic and clinical factors, including age, sex, race/ethnicity, symptom types, symptom severity, and duration of symptoms. The RR, 95% confidence intervals and p-values will be reported.

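### The n of 63 behind the primary interval counts primary cases, one per affected household, not the drug-eligible, doubly positive individuals in the primary denominator, so the stated ±0.12 is not supported for that endpoint

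*Protocol*

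**What the plan says.** Protocol XI makes precise estimation the primary objective, defines precision by the width of a 95% confidence interval, and bounds the half-width by 1.96 × 0.5/√n. There n is everyone who tests positive for influenza. The section then states: "With 250 households participating and an attack rate of 25% we expect 63 individuals with confirmed influenza infection". From this it concludes that the half-width is 0.12 or less.

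The 25% comes from Protocol II, where it applies to households: "25% are estimated to have an individual in the household diagnosed with influenza based on estimates from previous household studies". The table there, headed by household attack rate, lists 63 primary cases for 250 households and puts secondary cases in separate columns.

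Protocol III (Primary Outcome Measures) defines the endpoint as those reporting drug intake within 48 hours of onset, "divided by the total number of drug eligible individuals with both self-test positive influenza and laboratory-confirmed influenza".

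Three other provisions bear on the count:

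- Households need at least three members, but only some must be able to take the drug: "At least 2 household members meeting all individual inclusion/exclusion criteria listed below and willing to participate" (Protocol IV).
- The self-test is to be used only while symptoms have lasted less than 48 hours (Protocol V, Onset of Symptoms).
- The target of 250 is worded in two ways: "The goal is to have 250 households comply with full study procedures" (Protocol II) and "The goal is to enroll 250 households, with enrollment occurring prior to and during the annual influenza season" (Protocol IV, Study size).

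**The concern.** The n in the precision statement and the denominator of the endpoint are different populations. A primary case may be a member who cannot take baloxavir. An eligible case may have a false-negative self-test, reach the test after 48 hours, or lack a laboratory result. Each of these is outside the primary denominator but inside the 63. Neither document gives the drug-eligible share among cases. Self-test sensitivity is not given either; it is itself a secondary endpoint.

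This is the protocol's only sizing statement for its primary objective. SAP B5 does not fill the gap, because it sizes a two-arm cluster comparison of influenza incidence. At stake is whether the reader can rely on the stated precision, and which cases the primary proportion counts.

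**Working it through.** **Inputs from the documents.** 250 households (Protocol II and IV). Household attack rate 25%, with 20% and 10% as alternatives (Protocol II table). For secondary cases, the table note reads "Secondary attack rate 18-38%, secondary cases presented as a range based on these high and low bounds". At least 3 members per household, at least 2 of them eligible (Protocol II and IV). Half-width 1.96 × √(p(1−p)/n), which at p = 0.5 is the formula in Protocol XI.

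**Not in the documents, so assumed below.** Eligible share of household members; equal infection risk for members; share q of eligible cases that are both self-test positive and laboratory confirmed.

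**1. The plan's figure.** 250 × 0.25 = 62.5, rounded up to 63. 1.96 × 0.5/√63 = 0.1235, which rounds to 0.12. The arithmetic reproduces.

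**2. Slack.** At p = 0.5, n = 62 gives 0.1245 and n = 61 gives 0.1255, so losing two of the 63 breaks even the rounded figure. Smallest n under each criterion:

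| Criterion | p = 0.5 | p = 0.8 | p = 0.9 |
|---|---|---|---|
| Half-width rounds to 0.12 | 62 | 40 | 23 |
| Half-width 0.12 or less exactly | 67 | 43 | 25 |

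**3. The protocol's own attack-rate rows, before any restriction.**

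| Row | n | p = 0.5 | p = 0.8 | p = 0.9 |
|---|---|---|---|---|
| 25% | 63 | 0.123 | 0.099 | 0.074 |
| 20% | 50 | 0.139 | 0.111 | 0.083 |
| 10% | 25 | 0.196 | 0.157 | 0.118 |

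**4. Illustration: about one eligible case per affected household.** With K of m members eligible and secondary attack rate s,

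n = 63 × [K/m + (1 − K/m)(1 − (1 − s)^K)] × q.

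The first term is an eligible first case. The second is an ineligible first case followed by infection of at least one eligible member.

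- Lowest mix shown, 2 of 5, s = 0.18, q = 1: 63 × [0.4 + 0.6 × (1 − 0.82²)] = 63 × 0.5966 = 37.6.
- All members eligible, q = 1: 63.
- So with no testing loss n is about 38 to 63, and the half-width at p = 0.5 is 0.160 to 0.123.
- With q = 0.6 at the low end, 37.6 × 0.6 = 22.5. With q = 0.9 at the high end, 63 × 0.9 = 56.7. Half-widths are 0.206 to 0.130 at p = 0.5, 0.165 to 0.104 at p = 0.8, and 0.124 to 0.078 at p = 0.9.

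**5. Illustration: every eligible case counts, including secondary cases.** n = 63 × (K/m) × (1 + s(m − 1)) × q.

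- 2 of 5, s = 0.18, q = 0.6: 63 × 0.4 × 1.72 × 0.6 = 26.0, half-width 0.192 at p = 0.5.
- 5 of 5, s = 0.38, q = 0.9: 63 × 1 × 2.52 × 0.9 = 142.9, half-width 0.082 at p = 0.5.

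This ignores correlation within households. The mixes in steps 4 and 5 are examples, not limits of the design.

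**The case against.** A reader might infer that the true precision must be worse than ±0.12, or that the study is too small. The documents do not support that, for four reasons.

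- **A high proportion narrows the interval.** The primary hypothesis expects a large percentage, and at p = 0.8 or 0.9 far fewer than 63 cases suffice. This stands. However, Protocol XI offers its formula as a bound whatever the proportion.
- **All members may be eligible.** The household criteria allow this. With little testing loss, n then stays near 63.
- **Secondary cases could add to n.** Protocol III does not expressly exclude them. But Protocol II says "Once an eligible study participant receives BXM, no additional household members will be eligible to receive BXM", Weekly Monitoring in Protocol V repeats the limit for the household, and Protocol III counts people eligible to receive the drug. That wording leans toward leaving later cases out, though it fixes no time point. If they stayed in, they would almost certainly count as failures.
- **Full compliance may already be assumed.** If 250 means fully compliant households, self-test uptake and swab return are covered. Eligibility, false-negative self-tests and tests reached after 48 hours are not.

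It would also be too strong to call 63 a simple confusion of households with individuals. With one primary case per affected household, the two counts coincide. The gap lies in eligibility and double positivity.

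A further defence is that diagnosed in Protocol II means drug-eligible cases, as in the column headings of Table 1 (Timing of Data Collection). This is possible but not decisive, because the 25% is taken from outside household studies. On that reading only the double-positive loss remains: 63 × 0.6 to 63 × 0.9 is 37.8 to 56.7, or ±0.159 to ±0.130 at p = 0.5.

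Finally, this is a pilot and no decision rule depends on ±0.12. That limits the consequence but does not supply the missing link.

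**Conclusion.** The point holds as a lack of support, not as a demonstrated error. The count of 63 is reproduced correctly, but it is not an expected size for the primary denominator, and nothing in either document makes it one. At p = 0.5, the basis of the protocol's own bound, the figure tolerates the loss of one case after rounding and none if read exactly.

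How far precision would move depends on quantities that the documents do not give. Under the assumptions in the working, the worst-case half-width runs from about 0.21 to 0.13 with one eligible case per household and 60–90% doubly positive. It runs from about 0.19 to 0.08 if all eligible cases count and household correlation is ignored. The stated bound can be met with a high proportion, with all-eligible households and little testing loss, or with secondary cases included.

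This should be corrected because it is the stated precision of the primary objective. The effect is confined to that statement and to which cases are counted.

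**What to change.** **Protocol XI.** Replace 63 and the 0.12 bound with an expected n for the denominator defined in Protocol III. State the assumed drug-eligible share, self-test uptake and sensitivity, and swab return. Say whether 250 means households enrolled or households fully compliant, since Protocol II and IV differ. Give half-widths over the plausible n, for example:

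| n | p = 0.5 | p = 0.8 | p = 0.9 |
|---|---|---|---|
| 20 | 0.219 | 0.175 | 0.131 |
| 30 | 0.179 | 0.143 | 0.107 |
| 40 | 0.155 | 0.124 | 0.093 |
| 50 | 0.139 | 0.111 | 0.083 |
| 63 | 0.123 | 0.099 | 0.074 |

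Extend the table upward only if later household cases count.

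**Protocol III.** Reconcile the denominator with the one-delivery provision in Protocol II and in Weekly Monitoring (Protocol V). Say whether a drug-eligible case arising after a household member has received baloxavir is counted. If so, allow for household correlation in the interval.

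**Cost.** Wording only, with no extra participants. The stated precision may become less favourable.

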For the secondary endpoints of symptom duration and severity, drug eligible and drug ineligible participants will be analyzed separately. Symptom severity will be measured on a 4-point scale (0 = no symptoms, 1 = mild, 2 = moderate, 3 = severe) for each influenza-associated symptom the participant reports experiencing. Influenza-associated symptoms the participant does not report as experiencing will be coded as 0. An additional analysis will be conducted comparing secondary endpoints for drug eligible, influenza-infected study participants that received and initiated treatment within 48 hours of symptom onset and those that initiated treatment later than 48 hours. Kaplan-Meier curves will be used to present and analyze time to resolution of symptoms, defined as the time when the influenza-positive participant reports experiencing no respiratory or systemic symptoms. For study participants who received BXM, a Cox proportional hazards model will be used to calculate the hazard ratio, 95% confidence interval, and p-value for symptom duration by group (therapy within 48 hours of symptom onset, and therapy after 48 hours of symptom onset). The analysis of drug ineligible study participants will use a similar approach but will cluster by household and use a robust variance for computing confidence intervals and p-values. For BXM recipients, symptom severity will be compared between groups (therapy within 48 hours of symptom onset, and therapy after 48 hours of symptom onset) using proportions for categorical measures of severity and Pearson's chi-square test, as well as using ordinal regression. As above, the analysis using ordinal regression of drug ineligible study participants will cluster by household and use a robust variance for computing confidence intervals and p-values.

For the secondary endpoints of maximum viral titer and duration of viral RNA detection, we will use t-tests or nonparametric alternatives and linear regression to assess maximum viral titer and Kaplan-Meier curves and Cox proportional hazards models to assess duration of viral RNA detection.

Interim Analysis

This study is being conducted over the course of one influenza season. Therefore, an interim analysis will not be performed.

Antiviral resistance analysis

The secondary outcome data regarding emergence of BXM resistance will be reviewed at the end of the influenza season via genome sequencing of the viral RNA.

Health economic analysis

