Success = Participant initiated on antiviral therapy within 48 hours of symptom onset
Failure = Participant is not initiated on antiviral therapy (**more than 48 hours** after symptom onset *or* participant **never** initiates antiviral therapy)

Table 1. Estimated secondary attack rates for planned 2019-2020 study aim on household transmission dynamics.

The study is being conducted in the Seattle, WA area over one influenza season. The goal is to enroll at least 250 (up to 1,000) households. Of these, 25% are estimated to have an individual in the household diagnosed with influenza based on estimates from previous household studies.^{23, 28-29}

A table for influenza attack rates by household size is provided below.

Household attack rate	Total households enrolled	Primary cases	Secondary cases (mean household size 5)	Secondary cases (mean household size 4)	Secondary cases (mean household size 3)
25%	250	63	45-96	34-72	23-48

20%	250	50	36-76	27-57	18-38
10%	250	25	18-38	14-29	9-19
Mean household size includes case.					
Secondary attack rate 18-38%, secondary cases presented as a range based on these high and low bounds.³⁰⁻³²					

Incidence Density

Using time-specific variables such as date of enrollment, weekly symptom diaries and questionnaires, Incidence Density (ID) will be calculated, defined with the following formula:

Incidence Density =

Number of participants that successfully initiate antiviral therapy within 48 hours of symptom onset (among participants who have a cough and self-test positive for influenza)

Total person-days

Model

The proportion of individuals that 1) test positive and 2) receive and initiate treatment within 48 hours of symptom onset using home-based self-test and delivery methods will be analyzed with a binomial regression GLMM with a log link. The outcome follows a binomial distribution, with the number of successes in a series of n independent Bernoulli trials, where each trial has probability of success p . Successes here are defined as an individual successfully initiated on antiviral therapy within 48 hours of symptom onset using home-based self-test to diagnose influenza and home delivery of antivirals. The model is defined below:

Incidence proportions of influenza will be presented in tables.

A formal statistical comparisons between study periods (control vs. intervention) will be performed using a Wald test of the hypothesis

$H_0: RR=1$

$H_a: RR \neq 1$

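### The primary endpoint can include several drug-eligible cases from one household, but neither document specifies a usable household-level variance for it or says how cases after the household's single baloxavir course are counted

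*Protocol*

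**What the plan says.** Protocol III (Primary Outcome Measures) defines the primary proportion as on-time initiators "divided by the total number of drug eligible individuals with both self-test positive influenza and laboratory-confirmed influenza". It does not restrict this to the first case in a household. Protocol IV (Household inclusion criteria) requires "At least 2 household members meeting all individual inclusion/exclusion criteria listed below and willing to participate", so a household can supply more than one record.

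Protocol XI bases precision on a half-width of 1.96 × 0.5/√n, "where n is the number of individuals who test positive for flu", and adds: "With 250 households participating and an attack rate of 25% we expect 63 individuals with confirmed influenza infection". For the risk ratios it says "Binomial regression with log link will be used to calculate the relative risk of receiving and initiating treatment within 48 hours". No household term or robust variance is attached to either. Later in the same section, for symptom duration, it says "The analysis of drug ineligible study participants will use a similar approach but will cluster by household and use a robust variance", and it repeats this for ordinal severity.

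SAP B6 (Model) puts the primary endpoint in a binomial GLMM fitted in lme4, with a random-effects term in the equation. It does not say what the random effects are grouped by, and the same paragraph describes the outcome as binomial "with the number of successes in a series of n independent Bernoulli trials".

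Protocol II sets the one-course rule: "Once an eligible study participant receives BXM, no additional household members will be eligible to receive BXM". Protocol V (Weekly Monitoring) repeats it.

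**The concern.** Two drug-eligible members of one household share a phone, reporting habits and a delivery address, which would make their outcomes alike. The one-course rule pulls the other way: once one member has been treated, no later member can succeed. An interval that treats these people as independent has the wrong width, and the direction depends on which mechanism operates.

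Protocol XI makes precise estimation of this proportion the primary objective, so the interval is the main result. The risk-ratio intervals and p-values rest on the same assumption. An analyst with both documents could not tell whether to fit a model with no household term (Protocol) or a mixed model with an unstated grouping (SAP). The SAP is dated 10/8/19 and Protocol 3.1 January 14, 2020.

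**Working it through.** **1. The plan's own figure.** 250 × 0.25 = 62.5, stated as 63. Half-width = 1.96 × 0.5/√63 = 0.1235, which rounds to the stated 0.12. This count is one case per affected household, so the mean cluster size is 1 and the design effect is 1. Clustering does not alter it.

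**2. How many extra cases could enter.** At a 25% household attack rate, the table in Protocol II gives 23 to 96 secondary cases (18–38% secondary attack rate, mean household size 3 to 5) beside the 63 primary cases. The documents do not say how many of these would be drug eligible.

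**3. Two readings of the denominator after a household's course is used.**
- Later cases stay in as failures. Protocol III counts all drug-eligible doubly positive people, and Protocol IV sets drug eligibility by age, weight and exclusions, none of which changes when another member is treated.
- Later cases leave. Protocol III speaks of people eligible to receive the drug, Protocol II says later members no longer are, and Protocol X defines drug ineligible as not able to receive it.

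**4. Later cases stay in as failures.** Simulation with 2,500 runs per scenario and 63 affected households. Assumed inputs: first drug-eligible case treated on time 80%, late 5%; 1 to 3 other eligible members. The 18% and 38% attack rates are the Protocol's.

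| Other eligible members | Attack rate | Independence SE | True SD | Ratio |
|---|---|---|---|---|
| 1 | 18% | 0.0529 | 0.0471 | 1.12 |
| 1 | 38% | 0.0521 | 0.0398 | 1.31 |
| 2 | 18% | 0.0523 | 0.0428 | 1.22 |
| 2 | 38% | 0.0474 | 0.0309 | 1.53 |
| 3 | 18% | 0.0503 | 0.0385 | 1.31 |
| 3 | 38% | 0.0425 | 0.0255 | 1.67 |

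As half-widths, the first row is 1.96 × 0.0529 = 0.104 against 1.96 × 0.0471 = 0.092; the last is 0.083 against 0.050. Repeat runs put the excess at 11 to 67%, and adding a shared household effect at ICC 0.29 left it in that range. Nominal 95% intervals covered 96 to 99.8%.

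The proportion is also capped, because a household can have at most one success. If all secondary cases are drug eligible, the maximum is 63/(63 + 23) = 73%, falling to 63/(63 + 96) = 40%.

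**5. Later cases leave the denominator.** Same assumptions. Only about 2 to 7 of the 63 households then contribute more than one case. Independence SE / true SD is 0.96–1.02 with no shared household effect and 0.90–0.96 with a latent ICC of 0.29.

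**6. The usual clustering argument, ignoring the rule.** Design effect = 1 + (m − 1) × ICC. With 0.29 and all secondary cases eligible:
- 23 secondary cases: m = 86/63 = 1.37, design effect 1.11, half-width 0.106 → 0.111.
- 96 secondary cases: m = 159/63 = 2.52, design effect 1.44, half-width 0.078 → 0.093.

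**7. Does household-robust variance work?** It came within about 3% of the true SD in the six scenarios of step 4 and in six matching scenarios with no rule and ICC 0.29 (coverage 92.5–94.8%).

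**The case against.** The strongest reply is that the SAP does provide for dependence. It specifies a mixed model, and independent Bernoulli trials can be read as independence conditional on the random effects. That stands in part: a reader might infer that the plan clusters by household only for drug-ineligible participants, and the SAP's random-effects term does not support that. What remains is that the grouping is unnamed and the independence statement is unqualified.

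Nor does the household clustering for drug-ineligible participants in Protocol XI show that the authors overlooked the same issue elsewhere. The unclustered comparisons there concern baloxavir recipients, and a household has at most one.

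A reader might also infer that the intervals are too narrow. Switching the one-course rule off and using ICC 0.29 gives coverage of about 89–93%. The rule is in the Protocol, however, and 0.29 is the SAP B5 value for influenza incidence, not for treatment within 48 hours. Part of the shortfall is the Wald interval itself, which covered 0.936–0.944 with fully independent data.

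Finally, a household random intercept cannot represent negative within-household correlation. It would be tempting to add that its variance would be estimated at zero; no such model was fitted, so that is not claimed.

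**Conclusion.** The gap is real and of moderate severity. The denominator can hold several people from one household, the Protocol's primary analysis ignores this, and the SAP's model is too incompletely specified to correct it.

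It would be wrong to infer that the stated ±0.12 is in error; it rests on one case per affected household and reproduces. The error lies in the analysis interval, and its size and sign turn on the unstated denominator. The independence SE is about 11–67% too large if later cases count as failures, and roughly 0–10% too small if they are excluded. These figures rest on the assumed 80% on time, 5% late, 1–3 other eligible members and an ICC of up to 0.29; the documents give none of these for this outcome. Nothing is claimed about the size or direction of error in the risk-ratio intervals.

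On the first reading the cap matters more than the variance, since a correct interval would sit around a proportion that could not approach 100%. This is a single-arm feasibility pilot with a descriptive primary proportion, so the point does not block the study.

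**What to change.** 1. Settle the denominator first. In Protocol III and XI and SAP B6, state whether it is all drug-eligible doubly positive cases or only those arising while the household can still receive baloxavir. Reconcile this with Protocol II, V (Weekly Monitoring) and X. The clinical rule itself need not change.
2. Name household as the cluster. Report the primary proportion with a household-robust or household-bootstrap 95% interval, and the risk ratios with household-robust variance, for example modified Poisson or GEE with an independence working correlation.
3. Reconcile Protocol XI with SAP B6 so that one model is specified. Remove the independence wording, and do not rely on a household random intercept alone, which cannot represent the negative dependence that arises if later cases count as failures.

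The cost is wording in both documents and one option in the analysis code. No additional data are needed.
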